#### 3.6 Outcomes of interest:

#### **Primary outcome**

The primary outcome will be the between–group change in MetS prevalence after 3 months from start of intervention.

The 2009 Joint Interim Statement (JIS) will be used to diagnose MetS, defined as the presence of  $\geq$  3 of the following 5 factors: increased WC (women:  $\geq$  80 cm), low HDL-C (women: <50 mg/dl (1.3 mmol/l) or treatment of low HDL-C), Hypertriglyceridemia  $\geq$ 150 mg/dl (1.7 mmol/l) or treatment, elevated BP (systolic BP  $\geq$  130 mmHg and/ or diastolic  $\geq$ 85

mmHg or treatment for hypertension) and elevated fasting blood sugar (FPG  $\geq$  100 mg/dl (5.6 mmol/l) or diabetes mellitus or treatment[3]

The European cutoffs for waist circumference will be used as recommended by WHO because of the unavailability of population/country specific WC cutoffs for sub-Saharan Africans [3] or Uganda.

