#### Secondary outcomes

The secondary outcome will be the within - and between group variations in each of the following variable measured.

- dietary habits and behaviors (salt intake, fruits and vegetables intake, fat intake,
- anthropometric (weight, WC and BMI)
- cardio-metabolic (hypertension, blood glucose, triglycerides, HDL)
- nutrition knowledge
- lifestyle (physical activity, alcohol intake, cigarette smoking)

Mean change in parameters across the comparison and intervention groups will be determined. The measurement of the outcomes will be conducted before and at the end of the activities to determine the effect of the intervention.

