#### **Data Analysis**

The data for participants who attend less than 60 % of their respective intervention sessions will be excluded from analyses.

Participants with attendance rates below 60% in the intervention sessions will not be included in the analyses.

The analyses will be conducted using Stata statistical software (SE/ 14.0, StataCorp, College Station, TX, USA. Variables will be expressed using descriptive analysis (means and SD). The baseline information for both comparison and intervention groups will be statistically compared regarding all influencing factors at baseline and end line (12 weeks). The chi-square test will analyse for differences in categorical outcomes, including baseline study characteristics, metabolic risk factors (waist circumference (WC), blood pressure (BP), triglycerides, fasting blood sugar(FBS), and high-density lipoprotein (HDL) Cholesterol),

and other factors including dietary habits such as fruits and vegetable intake, and food groups consumed. Behaviours, including smoking, alcohol intake, and physical activity, will also be analysed.

The Student T test for independent samples and variance analysis (ANOVA) will compare cardio-metabolic parameters (and their variations - to find any differences between findings) between the intervention group and the comparison group at the baseline and end of the intervention (after-before).

A 2 factor (2 x 2; group x time) repeated measures analysis of variance (ANOVA) will be performed for each dependent variable and a 1-way ANOVA will be used to assess the significance of differences between groups on the dependent variables assessed. Tukey's post hoc analysis will be performed if there is a significant finding. The T test for paired data will be applied to investigate within –group variable variations (after-before). Statistical significance will be set at p < 0.05.

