Linear relationships will be estimated using Pearson correlation (crude model) to examine the associations between changes in variables, expressed as percentage of change ((endpoint - baseline value)/baseline value × 100). A multilevel generalized linear mixed model (GLMM) will be performed to identify the contribution of changes in time /round (baseline, end-line) and group (control, intervention) to changes in metabolic parameters (BP, WC, HDLC, FBS and Triglycerides) independent of other factors (education level, age, occupation etc). The model allows for the analysis of data with repeated measures, particularly baseline and end-line measurements for each individual. It also assesses the effects of the intervention and accounts for the correlation between observations within individuals due to repeated measures, as well as the clustering of individuals within the control and intervention groups.

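### The crude correlations of percentage change are undefined where a baseline is zero, and if pooled over arms they can reflect the intervention effect alone

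*Protocol*

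**What the plan says.** The Data Analysis part of protocol section 3.9 plans Pearson correlations, labelled a crude model, "to examine the associations between changes in variables, expressed as percentage of change". With its formula, the change is "expressed as percentage of change ((endpoint - baseline value)/baseline value × 100". The sentence does not list the variables, does not limit them to metabolic measures, gives no rule for a zero baseline and does not mention study arm.

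The secondary outcomes in section 3.6 include "lifestyle (physical activity, alcohol intake, cigarette smoking" and "dietary habits and behaviors (salt intake, fruits and vegetables intake, fat intake". The sentence after the correlation plan names a narrower set, "changes in metabolic parameters (BP, WC, HDLC, FBS and Triglycerides", but does so for the mixed model.

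The t tests in the same section use the simple difference: they compare cardio-metabolic parameters and their variations "between the intervention group and the comparison group at the baseline and end of the intervention (after-before". The percentage scale appears only in the correlation analysis, and no reason is given for it.

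**The concern.** There are two separate difficulties.

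- **Scale.** The formula divides by the baseline value. Several secondary outcomes can be zero at baseline. A woman who reports no activity, or no fruit and vegetables, has no percentage change and would leave any correlation that uses that measure. She is also someone the education and activity sessions aim to change. A small non-zero baseline turns an ordinary change into a very large percentage, and a Pearson coefficient is sensitive to such values.
- **Missing adjustment.** The correlation is crude. If the two arms are pooled and the intervention shifts both variables, the two changes will correlate across the whole sample even when they are unrelated within each arm. A reader could take this as evidence that change in one variable drives change in the other, when it only restates the arm effect.

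At stake is the interpretation of an exploratory analysis, not the trial's main result.

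**Working it through.** The protocol gives no figure for this analysis, so there is none to reproduce.

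**1. Zero and near-zero baselines.** The formula is (endpoint − baseline)/baseline × 100. As an illustration, take three women who each gain 90 minutes of activity per week:

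- from 150 to 240: 90/150 × 100 = 60%
- from 10 to 100: 90/10 × 100 = 900%
- from 0 to 90: 90/0, undefined

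**2. Women lost.** The protocol does not give the share with a zero baseline, so a range is assumed. The total of 120 comes from section 3.7.

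| Assumed share at zero | Women lost (120 × share) | Women left |
|---|---|---|
| 5% | 6 | 114 |
| 10% | 12 | 108 |
| 20% | 24 | 96 |
| 40% | 48 | 72 |
| 60% | 72 | 48 |

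The five metabolic components have strictly positive baselines, so for them the loss is 0 of 120.

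**3. Does percentage change weaken the correlation?** This was simulated with 120 women, 2,000 replicates, log-normal baselines and an assumed true correlation of 0.4. The true correlation was set on the absolute changes in the additive case and on the log changes in the proportional case. Mean Pearson r, absolute versus percentage change:

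| Baseline CVs of the two variables | Additive change: absolute / percentage | Proportional change: absolute / percentage |
|---|---|---|
| 0.12 and 0.12 | 0.40 / 0.40 | 0.39 / 0.40 |
| 0.12 and 0.5 | 0.40 / 0.36 | 0.35 / 0.39 |
| 0.5 and 0.5 | 0.40 / 0.35 | 0.33 / 0.39 |
| 0.12 and 1.0 | 0.40 / 0.29 | 0.27 / 0.35 |
| 0.5 and 1.0 | 0.40 / 0.26 | 0.25 / 0.36 |

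Percentage change lowers r when change is additive and gives the higher r when change is proportional to baseline. It makes almost no difference for measures with little relative variation. The effect has no fixed sign.

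**4. Pooling over arms.** Suppose there is no within-arm correlation, the arms are equal in size, and the intervention shifts both changes by d within-arm SDs. The between-arm part adds d²/4 to each variance and to the covariance, so the size of the pooled correlation of absolute changes is

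r = (d²/4)/(1 + d²/4).

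- d = 0.5: 0.0625/1.0625 = 0.06
- d = 0.8: 0.16/1.16 = 0.14
- d = 1.0: 0.25/1.25 = 0.20

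With 104 women (the section 3.7 figure before the dropout allowance), simulation gives p < 0.05 in 9%, 29% and 55% of trials respectively. On the planned percentage scale at d = 0.8 the share is 14–28%, depending on the assumed baseline spread. After adjustment for arm it is about 4–5%, the nominal level.

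**The case against.** The strongest reply is that the text does not say behaviours enter these correlations. It says only that changes in variables are correlated. The outcomes named nearby are the five metabolic components, for which no baseline is zero. Section 3.9 also records some behaviours largely as categories, such as smoking status or being physically active or not, and a percentage change would not naturally be applied to those. This stands, and it makes the zero-baseline problem conditional. It does not remove it, because the wording sets no limit and the dietary and activity outcomes can be continuous.

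A reader might infer more than the documents support:

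- **That percentage change generally weakens the correlations and costs power.** It does so only if change is additive. If change is proportional to baseline, the absolute scale is the weaker one. The protocol says nothing about which applies and makes no power claim for this analysis.
- **That this is the only analysis linking behaviour to metabolic change.** The protocol never gives the correlations that purpose, and no objective depends on it.

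It can also be said that the analysis is openly labelled crude, that pooling over arms is not stated, and that the choice of variables and the handling of zeros may sit in a statistical analysis plan that is not shown. All of that is fair. The point rests on what the protocol does fix: the formula and the unadjusted method. A later plan would have to override both, not merely add detail.

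**Conclusion.** The point holds as a minor, partly conditional one. The fixed formula is undefined at zero and unstable near zero for any continuous behaviour that enters it. The number lost depends on a zero share the protocol does not give. For the metabolic components there is no loss.

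The lack of adjustment for arm matters whatever the scale, provided the arms are pooled. At assumed arm effects of 0.8 SD on both changes, 14–28% of trials of 104 women would show an association that does not exist within arms. The figure depends strongly on the assumed arm effect, as the range for d shows.

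The primary outcome, defined in section 3.6 as "The primary outcome will be the between–group change in MetS prevalence after 3 months from start of intervention", does not use percentage change. Neither do the sample size, the group comparisons or the mixed model.

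**What to change.** In the Data Analysis section, replace the crude percentage-change correlation with a linear model. The endline metabolic value is the outcome and the absolute change in the other variable is the explanatory term, adjusted for the baseline values of both variables and for arm. Use all women with both visits, so that nobody is lost through the choice of scale. If a correlation is preferred, report the partial correlation of absolute changes given both baselines and arm. Name the variables to be examined. Percentage change may stay as a descriptive measure for strictly positive variables.

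The cost is a few lines of wording, with the same data and the same software. The one downside is some loss of power if change is truly proportional to baseline.

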## Methods

This design is an individual randomized parallel-group study conducted among 120 participants (intervention (n=60) or control (n=60) groups) aged 15-49 in Wakiso district, central Uganda. The intervention will include an information leaflet, group nutrition education sessions, group physical activity sessions and group motivation interviewing sessions. The control group will receive the usual standard of care and referrals to the nearest health facilities.

Data will be collected at baseline and end line on sociodemographic factors, selected cardiovascular outcomes, biochemical outcomes, anthropometric measures, behavioural outcomes, and knowledge on MetS, using a household survey including a modified STEPS questionnaire.

Analyses will be conducted using Stata (SE/14.0). Descriptive analysis (means and SD) and Chi-square tests for categorical outcomes will compare baseline characteristics and metabolic risk factors between the intervention and the control groups. Student T-tests will be applied to continuous variables to assess cardio-metabolic parameters and their variations. Statistical significance will be at p < 0.05. A multilevel generalized linear mixed model (GLMM) will analyze the impact of time and study group on metabolic outcomes independent of other factors. The study will be conducted for 12 weeks following recruitment of the participants.

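### For the secondary component outcomes, the adjusted model does not say which coefficient is the treatment effect, no analysis is named as decisive, and within-arm change is tested as an outcome

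*Protocol*

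**What the plan says.** **Adjusted model.** Section 3.9 (Data Analysis) plans a multilevel GLMM "to identify the contribution of changes in time /round (baseline, end-line) and group (control, intervention) to changes in metabolic parameters", adjusted for factors such as education, age and occupation, with each woman's baseline and end-line values as repeated measures. Of its purpose the section adds: "It also assesses the effects of the intervention and accounts for the correlation between observations within individuals due to repeated measures". The Project Summary (Methods) says the model "will analyze the impact of time and study group on metabolic outcomes independent of other factors". Neither place gives an equation, names an interaction, or identifies the coefficient that measures the intervention.

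**Unadjusted between-arm tests.** The same section states: "A 2 factor (2 x 2; group x time) repeated measures analysis of variance (ANOVA) will be performed for each dependent variable". It also plans independent-samples t tests and ANOVA on the cardio-metabolic parameters and their changes, a one-way ANOVA between groups, and a Tukey step after a significant result.

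**Within-arm tests.** "The T test for paired data will be applied to investigate within"-group change from baseline to end-line. The threshold throughout is p < 0.05. Section 3.6 defines the outcome to match: "The secondary outcome will be the within - and between group variations in each of the following variable measured".

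No analysis is named as the one that decides.

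**The concern.** In a randomised trial measured before and after, the treatment effect is the between-arm difference at end-line, preferably given baseline, or equivalently a difference in change. In a model holding both visits as rows, that effect sits in the group-by-time term. A group main effect without the interaction averages the baseline difference, which randomisation makes zero in expectation, with the end-line difference. The one model that adjusts for covariates, and the only model named in the summary, is described by time and group alone. An analyst following that wording could report a diluted effect as the adjusted result.

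The paired tests raise a different problem. Change within one arm mixes the programme's effect with whatever would have happened anyway. Controls are referred for usual care (Section 3.3, Comparison) and receive healthy-lifestyle information (Section 3.10), so some change in both arms is plausible with no programme effect. Because within-arm change is itself part of the secondary outcome, a significant paired test in the intervention arm could be reported as a result. Several analyses of the same variables, with none leading, leave that choice open until the data are seen.

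**Working it through.** **Inputs.** From the protocol: two measurement times, 1:1 allocation, 60 per arm, 10% dropout or non-consent, p < 0.05. This gives 60 × 0.9 = 54 analysed per arm. Assumed, because the protocol does not give them: baseline to end-line correlation r = 0.6 (range 0.5 to 0.7), equal SDs at both visits, two-sided testing, and no clustering by session group. The protocol states no power for the component outcomes. Its totals of 98, 104 and 120 belong to the primary outcome, so there is no figure to reproduce here.

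**1. What a main-effects group coefficient estimates.** Let D be the end-line effect. With complete pairs, equal expected baselines and an identity link, the coefficient is the between-arm difference in each woman's two-visit mean: (0 + D)/2 = D/2. With the interaction included, the interaction term estimates D. Check by simulation (D = −4, SD 10, 60 per arm, r = 0.3, 0.5, 0.7, 0.8): the main-effects coefficient averaged −2.00, −2.03, −1.98, −1.97; the interaction averaged −4.04, −3.99, −3.99, −4.00.

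**2. Power, in SD units, normal approximation, n = 54 per arm, r = 0.6.**
- End-line adjusted for baseline (ANCOVA): SE = √(2(1 − r²)/n) = √(1.28/54) = 0.154. The effect giving 80% power is 2.80 × 0.154 = 0.431.
- Change score: SE = √(4(1 − r)/n) = √(1.6/54) = 0.172. 0.431/0.172 = 2.51, power 71%.
- Main-effects group coefficient, targeting D/2 = 0.216: SE = √((1 + r)/n) = √(1.6/54) = 0.172. 0.216/0.172 = 1.25, power 24%.

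The change-score and main-effects SEs coincide only because r = 0.6. Over the range of r, with the effect reset each time to give ANCOVA 80% power:

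| r | ANCOVA | Change score | Main-effects group term | ANCOVA variance ÷ change-score variance, (1 + r)/2 |
|---|---|---|---|---|
| 0.5 | 80% | 68% | 29% | 0.75 |
| 0.6 | 80% | 71% | 24% | 0.80 |
| 0.7 | 80% | 73% | 19% | 0.85 |

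**3. How many distinct between-arm analyses there are.** With two arms and two visits, the F statistic for the ANOVA interaction is the square of the change-score t statistic. A one-way ANOVA on the two arms' changes is that test again, and Tukey with two groups adds nothing. These are redundant with one another, not in conflict.

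**4. Paired tests when the programme has no effect.** Assume both arms drift by −2 (SD 10, 60 per arm). The SE of mean change is 10√(2(1 − r))/√60.
- r = 0.5: SE 1.29, chance of significance in one arm 0.332, so exactly one arm is significant with probability 2 × 0.332 × 0.668 = 0.44.
- r = 0.7: SE 1.00, chance 0.503, so 2 × 0.503 × 0.497 = 0.50.

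For drifts of −1 and −3 the probabilities are 0.21 and 0.47 at r = 0.5, and 0.28 and 0.27 at r = 0.7. Reading the two arms' paired tests side by side would therefore often suggest a difference where none exists.

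**The case against.** **The interaction is not excluded.** A reader might infer that the GLMM definitely omits it and halves the effect. The text does not support that. It gives no equation, it says the model assesses the intervention, and listing fixed effects is ordinary SAP content. If change itself were the modelled outcome, the group coefficient would be the full effect, although that fits poorly with a time factor and baseline rows. What stands is that the protocol names time and group in two places, while it does write out group-by-time for the ANOVA, and leaves the treatment coefficient unidentified. The halving is conditional on a main-effects fit, and is not exactly half with a non-identity link or incomplete pairs.

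**The full effect is already planned.** This is correct. The group-by-time ANOVA and the change-score comparison both estimate it, and being unadjusted does not bias them under randomisation. A reader might infer that the change-score tests mislead. They do not; they are only less precise than baseline adjustment.

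**Regression to the mean.** A reader might infer that selecting women for MetS makes the paired tests falsely significant at some known high rate. The protocol does not establish this. Women come from an earlier survey database (Section 3.5), and measurements are taken at a trial baseline before the intervention (Section 3.9). If that baseline is fresh, much of the regression would precede it. Section 3.6 requires only three of five components, so women are not selected on every one. Section 3.7 mentions screening without saying whether the thresholds are re-applied. Residual regression to the mean is possible, but its size is unknown. The objection to paired tests does not depend on it: any change common to both arms is enough.

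**Conclusion.** The point holds in a limited form. For the continuous component outcomes, the only adjusted analysis is specified too loosely to say what it estimates, no analysis is designated as decisive, and within-arm change has the status of a tested outcome.

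Fitted with main effects only, the GLMM group term would target D/2, with 19% to 29% power where baseline adjustment has 80% (r = 0.7 to 0.5). Fitted with the interaction and separate baseline means, it would recover the full effect. The planned unadjusted between-arm tests are valid; relying on them instead of baseline adjustment costs roughly 7 to 12 percentage points of power over the same range. The paired tests answer no between-arm question.

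The power figures rest on the assumed correlation, equal SDs and independence between women; the drift figures also rest on an assumed drift and SD. The between-arm change in MetS prevalence, the primary outcome, is not touched, so this is a moderate issue and does not threaten the main result.

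**What to change.** - Name one analysis for each continuous component outcome: the 12-week value compared between arms, adjusted for its baseline value. Equivalently, keep the GLMM with a group-by-time term and a common baseline mean. The planned covariates can stay.
- State that this between-arm contrast, with its 95% CI, is the treatment effect.
- Drop the one-way ANOVA and the Tukey step as redundant. The change-score t test and the group-by-time ANOVA are then not needed as separate tests; if kept, label them supportive.
- Reword the secondary outcome in Section 3.6 as the between-arm difference, and report within-arm change as means with SDs and no p-values.
- Make the GLMM description in the Project Summary match.

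The cost is wording only: no extra data, visits or participants. The loss is that within-arm p-values can no longer be reported.

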#### **3.0 DESIGN AND METHODS**

#### 3.1 Study Design:

The study design is an Individual Randomized Parallel-Group Trial study with both an intervention group and a control group in Wakiso district, Central Uganda. All women with Metabolic Syndrome identified in our baseline study will be randomized to either intervention and control groups. The intervention will be administered in 5 groups of 12 participants.

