#### Package of the group motivation interviewing sessions

3 sessions of group motivation interviewing (MI) will be held monthly over 3 months in groups of approximately 12 participants covering various topics, including goal setting, factors that motivate lifestyle and behavioural change, relapse and its management, coping strategies and support, eating habits at various settings. Discussions will be held on relevant topics using MI techniques.

**Comparison:** In the comparison group, participants with MetS will be subjected to only usual standard of care with no specific individualized interventions. This will include referral of the participants to the usual health care facilities for management of their conditions as per the existing routine health facilities protocols. This is for purposes of controlling for possible changes in outcome variable due to other influences or behaviours.

Effort will be undertaken to reduce non-adherence in intervention group through evaluating questionnaires and meeting attendance, use of paper and phone reminders, provision of information about study objectives and planned meeting schedules, and reinforcement of the need for compliance during follow up meetings.

 Table 2: Summary table for the intervention and non-intervention arms

No.	Intervention arm	Control arm
1.	Participants =60 women of reproductive age with MetS divided into 6 groups at baseline	Participants =60 women of reproductive age with MetS (no groups) at base line
2.	Intervention and duration: One hour of weekly group nutrition education seminar sessions offered for 12 sessions in 3 months and One hour of monthly group motivational interviewing sessions offered for 3 sessions undertaken for 3 months.	Duration of follow up: Usual standard of care in nutrition education varies depending on either inpatient or outpatient setting
	Behavioral change for dietary intake and physical activity enhanced by, motivation interviewing	Usual standard of care in nutrition education and counselling. There is limited or no focus on Motivational Interviewing for behavioural cchange
	Delivered by: Nutritionists and health workers using a tailor made curricular guide and materials for MetS	Delivered by: Nutritionists and health workers using nutrition guides and materials for management of malnutrition (under and over nutrition)

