#### **3.7 Sample size Determination**

#### Sample size for participants with Metabolic Syndrome (Primary outcome variable)

Using Power analysis computation of sample size with G.Power 3.1.9.4 software. The estimates will be based on a significance level of 5% and power of 80% to detect a difference between-group of 0.20 in MetS prevalence after 3 months intervention. A sample size of 98 is obtained. After accounting for design effect the sample size is 104. Assuming a dropout rate and failure to consent rate of 10%, 120 participants will be needed in total. 60 participants in the intervention and 60 in the non- intervention groups.

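### The planned analysis does not model the intervention session groups: its tests assume independence, and the mixed model appears to cluster women by trial arm

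*Protocol*

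**What the plan says.** **Delivery.** Section 3.1 states: "The intervention will be administered in 5 groups of 12 participants". The dosage text in section 3.3 repeats five groups of about 12, each supervised by one nutritionist, with weekly sessions over three months. Table 2 differs on the count: 60 "women of reproductive age with MetS divided into 6 groups at baseline". For controls the same table has 60 "women of reproductive age with MetS (no groups) at base line". Women are randomised individually, 1:1.

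**Sample size.** Section 3.7 aims to "detect a difference between-group of 0.20 in MetS prevalence after 3 months intervention". It obtains 98, raises this to 104 for a design effect, and arrives at 120 after dropout and non-consent. It gives no ICC, no cluster size and no reason for the design effect.

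**Analysis.** Under Data Analysis, "The chi-square test will analyse for differences in categorical outcomes". Independent and paired t tests, one-way ANOVA and a group-by-time repeated-measures ANOVA are planned for continuous measures, and "Statistical significance will be set at p < 0.05". A multilevel generalized linear mixed model is then planned for blood pressure, waist circumference, HDL cholesterol, fasting glucose and triglycerides. In that paragraph group is defined as control or intervention. The model is said to handle repeated measures within a woman, "as well as the clustering of individuals within the control and intervention groups".

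**The concern.** This is a partially nested trial. Women in one arm share sessions and facilitators for 12 weeks, and women in the other do not. If some session groups do better than others because of who leads them or how the group works together, outcomes within a group are correlated and the intervention mean is less precise than 60 independent women would make it.

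Nothing in the stated analysis picks this up. The simple tests have no cluster term. The mixed model has a level for the woman and, above it, what reads as the arm. Arm has two levels and is the comparison of interest, so naming it as a cluster adds no information about variation between session groups.

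The primary outcome is the most exposed. MetS prevalence is not on the mixed model's outcome list in Data Analysis, so the only stated test that fits it is the unadjusted chi-square. At stake are the nominal 5% level and the coverage of confidence intervals for the primary outcome and the components.

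**Working it through.** **Inputs from the protocol:** 60 women per arm; 5 groups of 12 (section 3.1) or 6 groups, hence 10 each (Table 2); no groups among controls; 5% significance level; 98 raised to 104. **Assumptions:** the ICC, which is not stated and is taken over a range; a two-sided test.

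**1. The plan's own figure.** Neither the control-arm prevalence nor the sidedness is given, so 98 cannot be confirmed from the stated inputs. The usual two-proportion formula with 80% power gives 98 for 95% versus 75% two-sided, and also for 90% versus 70% one-sided.

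**2. The ICC implied by the design effect.** 104/98 = 1.061.
- Clustering in the intervention arm only, groups of 12: 1 + 11 × ICC/2 = 1.061, so ICC = 2 × 0.0612/11 = 0.011.
- Clustering in both arms: 1 + 11 × ICC = 1.061, so ICC = 0.0612/11 = 0.0056.

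**3. Variance ratio.** With equal arms and clustering in one arm, the true variance of the arm difference over the variance that an independence test assumes is

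R = [1 + 1 + (m − 1) × ICC]/2 = 1 + (m − 1) × ICC/2.

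Actual two-sided type I error = 2 × [1 − Φ(1.96/√R)].

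| ICC | R, 5 groups of 12 | √R | Type I error, 5 of 12 | Type I error, 6 of 10 |
|---|---|---|---|---|
| 0 | 1.000 | 1.00 | 5.0% | 5.0% |
| 0.011 | 1.061 | 1.03 | 5.7% | 5.6% |
| 0.05 | 1.275 | 1.13 | 8.3% | 7.7% |
| 0.10 | 1.550 | 1.24 | 11.5% | 10.4% |

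The √R column is the factor by which the true standard error exceeds the one used.

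**4. Check by simulation, 5 groups of 12, ICC 0.011, 0.05 and 0.10.**
- t test (60,000 runs each): 5.7%, 8.4%, 11.4%.
- Chi-square with beta-binomial group rates at a common prevalence of 85% (200,000 runs each): 5.5%, 8.0%, 11.4%. With no clustering this test rejected in 4.7%.

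**5. Does modelling the groups help?** For a continuous outcome, session-group means were compared with individual controls using Satterthwaite degrees of freedom. At non-zero ICCs from 0.011 to 0.10, simulated type I error was 5.3–5.5% with 5 groups of 12 and 5.1–5.2% with 6 groups of 10.

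**The case against.** - **A reader might infer that type I error definitely exceeds 5%.** The documents do not support that. They state no ICC, and 0.05 and 0.10 are assumptions. The one anchor, the design effect, points to about 0.011 at most with groups of 12, where the excess is under one percentage point. The excess also needs a particular cause: session groups or facilitators with genuinely different effects. Correlation from area of residence is shared by both arms and broken by individual randomisation. A simulation with five areas, ICC 0.011 to 0.10 and unadjusted tests of proportions rejected in 4.5–5.3%. This objection stands in full and makes the size conditional.
- **A reader might infer that the clustering phrase can only mean the arms, or that a random intercept for arm is specified.** Neither is certain. The wording may be a loose description of a fixed arm effect. What stands is that the same paragraph defines group as the two arms and that controls have no session groups, so arm is the natural reading, and no session-group level is named anywhere.
- **A reader might infer that the design effect was put in for the session groups, so that sample size and analysis contradict each other.** Section 3.7 does not say what it is for. The link is plausible but not shown.
- **Cluster size.** Twelve is an upper figure. At 104/2/5 = 10.4 per group, type I error is 5.6%, 7.8% and 10.6% at the three ICCs.
- **Details belong in a SAP.** Random-effects structure often does, and one may exist. Here, however, the protocol itself names a clustering level, and that level does not fit the design.

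**Conclusion.** The concern holds in a conditional form. As written, no planned test accounts for session groups, and the level named above the woman is most naturally the trial arm, which cannot capture session-group correlation. The primary outcome is not on the mixed model's list.

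The numerical consequence rests on a positive ICC arising from shared delivery, 12 women per group, equal arms and a two-sided test. On those assumptions the nominal 5% becomes about 5.7% at the ICC the design effect implies for one-arm clustering, and 8.3% to 11.5% if the ICC is 0.05 to 0.10. With no such correlation there is no inflation.

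The conflict between 5 and 6 groups is a separate inconsistency. It is not evidence of inflation, but with so few clusters the count sets the degrees of freedom. Severity: should-fix.

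**What to change.** **Change the Data Analysis section as follows.**
- Replace clustering by arm with session group as the clustering level in the intervention arm only. Each control is her own cluster and arm is a fixed effect.
- Use a small-sample correction suited to 5 or 6 clusters: for example, Satterthwaite or Kenward-Roger degrees of freedom for continuous outcomes and a small-sample-corrected robust variance for MetS. The check above covers only a continuous outcome with Satterthwaite degrees of freedom, so the method chosen for MetS should be simulated before it is fixed.
- Apply this to MetS prevalence as well as the five components.
- State the assumed ICC and what the design effect in section 3.7 represents.
- Reconcile the five groups of section 3.1 and the dosage text with the six of Table 2.
- Record each woman's session-group ID during delivery; without it this analysis may be impossible later.

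**Cost.** One data field and revised wording. By the √R column, standard errors grow by about 3% at ICC 0.011, 13% at 0.05 and 24% at 0.10. Intervals widen further because the between-group variance has only about 4 degrees of freedom with five groups (5 with six) before adjustment. At the implied ICC the gain in type I error is small: the corrected analysis still ran at 5.3% with five groups, against 5.7% uncorrected. If groups follow area of residence, the session-group term will also absorb area differences and be somewhat conservative.
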